#### 1.0 Synopsis

Title	A Patient Experience Study with ABBV-444 for Symptom Relief and Tolerability		
Sponsor (Responsible Party)	AbbVie Inc		
Rationale and Background	ABBV-444 will be the asset used for this study to assess the patient experience.		
	However, there is a gap in our knowledge as to the effect of new formulation, ABBV-444, on patient symptom relief and product tolerability. As PROs are recognized as important measures for clinicians and patients, it is necessary to conduct a Patient Experience Study for ABBV-444.		
Research Question	What is the effect of ABBV-444 on patient symptom relief and product tolerability?		
Objectives and Endpoints	Primary Objective: To assess whether ABBV-444 will reduce patient symptoms evaluated by the Ocular Surface Disease Index (OSDI) questionnaire.		
	Secondary Objective: To describe the patient experience of ABBV-444 by Patient Eye Drop Experience Survey and effect of immediate symptom relief by the Current Symptom Survey		
	Primary Endpoints: Change from baseline in OSDI score at Day 30.		
	Secondary Endpoints:		
	
 
Patient Eye Drop Experience scores at Day 30
 
		
	
 
Change from baseline in symptom scores within 5 mins post administration of ABBV-444
 
		
	Exploratory Endpoints:		
	Patient Eye Drop Experience scores at Day 14		
	Change from baseline in OSDI score at Day 14		

Version date: 02 February 2023

#### Study Design

#### **Overall Study Design:**

A single center, open-label, single arm study (ABBV-444) enrolling approximately 40 patients.

#### **Inclusion/Exclusion Criteria for study population:**

Inclusion criteria are as follows;

- Participant must be  $\geq 18$  years of age
- Written informed consent and written documentation, in accordance with the relevant country and local privacy requirements, had been obtained prior to any study procedures
- Had used artificial tears for dry eyes within the past year
- Females of childbearing potential, with a negative pregnancy test result at Screening Visit; these patients must have been currently using a reliable form of birth control and have agreed to use a reliable form of birth control for the duration of the study
- OSDI score of ≥ 18 and ≤ 65 (based upon a 0 to 100 scale) at Screening and Baseline Visits Three consecutive tear breakup time (TBUT) tests ≤ 10 seconds in at least 1 eye at Day -7 (screening)
- Grade 1 to 4 (modified National Eye Institute [NEI] Grid, score range = 0 to 5) staining in at least 1 area of the cornea (5 areas examined) or conjunctiva (6 areas examined) that was related to dry eye in at least 1 eye at both at Screening and Baseline Visits
- Was able/agreed to continue to wear existing current spectacle correction during the study period (if applicable)
- Currently corrected distance visual acuity of at least 20/32
   Snellen equivalent in each eye using the 3-meter LogMar chart, with existing spectacle correction (if necessary) at Screening Visit
- If using any form of topical ophthalmic cyclosporine (i.e., RESTASIS®), lifitegrast 5% ophthalmic solution (Xiidra®), participants must be using the drops for ≥ 90 days prior to the Screening Visit and plan to continue without change for the duration of the study
- Intraocular pressure (IOP) ≤ 21 mmHg in both eyes for patients with primary open-angle glaucoma or ocular hypertension (OHT). Patients with primary open-angle glaucoma or OHT were included provided they were on stable monotherapy bilaterally with IOP controlled (≤ 21 mmHg) in both eyes. Any topical IOP-lowering medications must have had a start date of ≥ 3 months prior to Screening Visit date and dosage that was not expected to change during the study.

Version date: 02 February 2023

• Was able to follow study instructions and was likely to complete all required visits

[figure not shown]
#### Exclusion criteria are as follows:

- Have uncontrolled severe systemic disease that, in the
  assessment of the investigator, would put safety of the
  participant at risk through participation, or which would
  prevent or confound protocol-specified assessments (e.g.,
  hypertension and diabetes, Sjögren's syndrome, rheumatoid
  arthritis, systemic lupus erythematosus, immunodeficiency
  disease, etc.)
- Known allergy or sensitivity to the study products or their components
- Females who were pregnant, nursing, or planning a pregnancy
- Females of childbearing potential and who were not using a reliable method of contraception
- Current enrollment in an investigational drug or device study or participation in such a study within 30 days of entry into this study at Screening Visit
- Schirmer Test (with anesthesia) ≤ 2 mm in either eye at Screening Visit
- Patient anticipated contact lens wear during the study, or the patient had worn contact lenses in the last 3 months prior to Screening Visit
- Any scheduled or planned elective ocular or systemic surgery or procedure during the study, which in the investigator's opinion, may have impacted the patient's study participation
- At the Screening and Baseline visits, either eye has corneal staining score of 5 in any of the 5 zones or a total score of > 19 based on the modified NEI grading scheme (score range = 0 to 5; graded in 5 zones of the cornea for a total score range of 0 to 25) or conjunctival staining score of 5 in any of the 6 zones based on the modified NEI grading scheme (score range = 0 to 5 per zone)
- Use of systemic medications (over-the-counter, herbal, prescription, or nutritional supplements for dry eyes), which may have affected tear film or vision (including but not limited to the following: flax seed oil, fish oil, omega-3 supplements, cyclosporine, antihistamines, cholinergic agents, anticholinergics, antimuscarines, beta-blocking agents, tricyclic antidepressants, phenothiazines, estrogen-progesterone, and other estrogen derivatives), unless that medication had been used at the same dose for at least 3 months prior to screening and the dosage was not expected to change during the course of the study

Version date: 02 February 2023

- Presence of 1 or more of the following ocular conditions in at least 1 eye:
  - Active ocular infection or non-keratoconjunctivitis sicca (KCS) ocular inflammation
  - Active ocular allergy
- History of recurrent herpes keratitis or active disease within 6 months prior to Screening Visit
- Corneal disorder or abnormality that affected corneal sensitivity or normal spreading of the tear film (except superficial punctate keratitis)
- Severe blepharitis or obvious inflammation of the lid margin, which in the judgment of the investigator, may have interfered with the interpretation of the study results
- Keratoconjunctivitis sicca secondary to the destruction of conjunctival goblet cells, such as occurs with vitamin A deficiency or scarring such as that with cicatricial pemphigoid, alkali burns, Stevens-Johnson syndrome, trachoma, or irradiation
- Substantial non-KCS keratitis with overlying corneal stain or other significant corneal findings not directly related to dry eye; in addition, patients with dry eye signs/symptoms (e.g., filamentary keratitis) of a severity where topical monotherapy with an artificial tear would have been inappropriate
- Occlusion of the lacrimal puncta for either eye, with punctal plugs or cauterization < 3 months prior to Screening Visit
- History of prior ocular/ophthalmic surgery or trauma, which could affect corneal sensitivity and/or tear distribution (e.g., cataract surgery, laser-assisted in situ keratomileusis [LASIK], photorefractive keratectomy, or any surgery involving a limbal or corneal incision) within 6 months prior to at Screening Visit
- Patients who were currently using topical ocular medication or had used topical ocular medication within 2 weeks of Screening Visit; however, patients who were being treated bilaterally with the following could have been considered:
  - Current use of a marketed artificial tear, which was to have been discontinued at the Screening visit
  - Monotherapy for glaucoma or OHT using a prostaglandin analog, beta-blocker, alpha-2 agonist, or carbonic anhydrase inhibitors; any topical IOP-lowering medications must have had a start date of ≥ 3 months prior to Screening Visit and the dosage was not expected to change during the study

	If using any form of topical ophthalmic cyclosporine (i.e., RESTASIS®), lifitegrast 5% ophthalmic solution (Xiidra®), for less than 90 days prior to Screening Visit Patients who were currently being treated with both IOP-lowering medication and any form of topical ophthalmic cyclosporine (i.e., RESTASIS®) or lifitegrast 5% ophthalmic solution (Xiidra®) or generic of these medications cannot be enrolled  Patient had a condition or is in a situation, which in the investigator's opinion, may have put the patient at significant risk, may have confounded the study results, or may have interfered significantly with the patient's participation in the	
Sample size and Justification	This study is a descriptive non-hypothesis based study. 40 subjects will be enrolled in this study. Assuming a non-response rate of 10% at 30 days, there would be about 36 evaluable subjects.	
Statistical methods	Analysis of all data will be descriptive. Biometrical analysis will be conducted based on subject demographics. Arithmetic mean, median, standard deviation (SD), standard error of the mean (SEM), interquartiles, minimum, and maximum will be used for the description of the data. Descriptive p-values (paired t-test) will be calculated for changes during the observation period, if adequate.	

Version date: 02 February 2023

# 4.0 Background and Rationale

# 4.1 Background

Dry eye disease (DED) is a multifactorial disease of the ocular surface characterized by a loss of homeostasis of the tear film, and accompanied by ocular symptoms, in which tear film instability and hyperosmolarity, ocular surface inflammation and damage, and neurosensory abnormalities play etiological roles (Craig 2017).

To date, management and treatment of DED remains a large unmet medical need. Current mainstays include use of artificial tears and in more severe cases, tear retention (temporarily or permanently plugging the tear ducts) and anti-inflammatory therapies (Craig 2017). Artificial tears have been used for relief for symptoms of eye dryness (burning, irritation, and discomfort) and have proven to be safe and effective for lubricating and protecting the ocular surface from further irritation and relieving eye dryness symptoms.

There is a gap in our knowledge as to the effect of ABBV-444 on patient symptom relief, product tolerability and the patient eye drop experience. ABBV-444 is developed to meet the requirements of section 505G of the Federal Food, Drug and Cosmetic (FD&C) Act, including the over-the-counter (OTC) drug monograph and other applicable requirements, therefore ABBV-444 can be brought to market in the US via the OTC drug monograph

Version date: 02 February 2023

process. The OTC drug monograph process does not require a manufacturer to submit clinical trial data demonstrating safety and effectiveness of an individual drug, nor does it require an OTC drug to be approved by FDA prior to marketing.

#### 5.1 **Research Question**

There is no formal hypothesis as the nature of this study is to describe the effect of ABBV-444 on symptoms relief of dry eye, such as burning, irritation and, discomfort due to eye dryness, the onset of action of relief and the patient experience across various timepoints.

#### 5.2 **Study Objectives**

Evaluate the effect of ABBV-444 on symptom relief, product tolerability and the patient experience after product use over time in adult patients with dry eye (patients with symptoms of burning, irritation, discomfort due to eye dryness).

#### 5.2.1 **Primary Objective**

The primary objective is to assess whether ABBV-444 will reduce patient symptoms when evaluated by OSDI questionnaire.

#### 5.2.2 **Secondary Objectives**

The secondary objective is to investigate the patient eye drop experience of ABBV-444 and the eye drop onset of action using a VAS-Current Symptom Survey.

Version date: 02 February 2023

### 5.3 Study Endpoints

# 5.3.1 Primary Endpoint

The primary endpoint is the change from baseline in OSDI score at Day 30.

# 5.3.2 Secondary Endpoints

- Patient Eye Drop Experience scores at Day 30
- Change from baseline in symptom scores within 5 mins post administration of ABBV-444

# 5.3.3 Exploratory Endpoints

- Patient Eye Drop Experience scores at Day 14
- Change from baseline in of OSDI score at Day 14

# 6.0 Study Design

### 6.1 Overall Design

[figure not shown]
This prospective, minimally interventional study will aim to describe the effect of ABBV-444 on relieving dry eye symptoms, such as burning, irritation, discomfort due to eye dryness (via the OSDI scoring tool), the patient experience (via a Patient Eye Drop Experience Survey) and the onset of action of the eye drop (via the Current Symptom Survey) across various timepoints (Figure 1). This will be an open-label, 1-arm study in which eye drops will be administered bilaterally as needed but minimally twice a day. Approximately 40 patients are planned to be enrolled at 1 site. A screening period of up to 6 days will be conducted prior to the Baseline Visit. Patients will be instructed to not administer any drops at least 4 hours prior to Baseline Visit. There will be three surveys administered to the subjects throughout the course of the study at the following timepoints:

Version date: 02 February 2023

- 1. OSDI will be given at Screening Visit, Baseline, Day 14 and Day 30/Early exit; and
- 2. Patient Eye Drop Experience Survey at Day 14 and Day 30/Early exit; and
- 3. Current Symptom Survey at Day 1; T0 (pre-dosing), T30s, T1min, T3min and T5min post-dose.
- 4. Study Product Usage Questionnaire at Day 14 and Day 30/Early exitStudy treatment is 30 days where OSDI scores, Patient Eye Drop Experience Survey scores and Current Symptom Survey scores will be obtained at the time points listed above. To assess product usage and compliance, the Study Product Usage Questionnaire will be administered at the time points listed above. Data will be collected via a paper questionnaire, sent to Lumanity where outcomes will be computed as mean changes from their baseline values.

Figure 1. Study Schematic

**Table 1.** Study Activities

It is recommended these procedures are completed in order listed at each study visit.

Version date: 02 February 2023

Study Visit	Screening (Day -7)	Baseline (Day 1)	Day 14	Day 30/Early Exit
Visit Window	(-7 to -1 days)		(+/- 3 days)	(+/- 3 days)
Written informed consent	X			
Urine pregnancy test (for females of childbearing potential only)	X			
Demography	X			
Adverse Event Assessment	X	X	X	X
Study Product Usage Questionnaire			X	X
OSDI Questionnaire	X	X	X	X
Biomicroscopy	X	X		
Tear Breakup Time (with fluorescein)	X			
Corneal staining (modified NEI grading scheme, with fluorescein)	X	X		
Conjunctival staining (modified NEI grading scheme, with lissamine green)	X	X		
Schirmer Test	X			
Intraocular Pressure (Goldmann Applanation tonometer) a	X			X
ABBV-444 dispensed		X	X	
Current Symptom Survey b		X		
Patient Eye Drop Experience Survey			X	X
Used and unused ABBV-444 returned				X

For patients with primary open-angle glaucoma or ocular hypertension only

#### **Study Population** 6.2

The study population will consist of adult subjects with signs and symptoms of dry eye. The study will include 40 subjects with objective and subjective evidence of dry eye.

Conducted at T0 (pre-dosing), T30 sec, T1min, T3 min and T5 min post-dose.

Version date: 02 February 2023

#### 6.2.1 Inclusion Criteria

Patients that meet the following eligibility criteria will be included:

- Participant must be  $\geq 18$  years of age
- Written informed consent and written documentation, in accordance with the relevant country and local privacy requirements, had been obtained prior to any study procedures
- Had used artificial tears for dry eyes within the past year
- Females of childbearing potential, with a negative pregnancy test result at Screening; these patients must have been currently using a reliable form of birth control and have agreed to use a reliable form of birth control for the duration of the study
- OSDI score of ≥ 18 and ≤ 65 (based upon a 0 to 100 scale) at Screening and Baseline Visits
- Three consecutive tear break-up time (TBUT) tests ≤ 10 seconds in at least 1 eye at Screening Visit
- Grade 1 to 4 (modified National Eye Institute [NEI] Grid, score range = 0 to 5) staining in at least 1 area of the cornea (5 areas examined) or conjunctiva (6 areas examined) that was related to dry eye in at least 1 eye at both at Screening and Baseline Visits
- Was able/agreed to continue to wear existing current spectacle correction during the study period (if applicable)
- Currently corrected distance visual acuity of at least 20/32 Snellen equivalent in each eye using the 3-meter LogMar chart, with existing spectacle correction (if necessary) at Screening Visit
- If using any form of topical ophthalmic cyclosporine (i.e., RESTASIS®), lifitegrast 5% ophthalmic solution (Xiidra®), participants must be using the drops for ≥ 90 days prior to the Screening Visit and plan to continue without change for the duration of the study
- Intraocular pressure (IOP) ≤ 21 mmHg in both eyes at Screening Visit for patients with primary open-angle glaucoma or ocular hypertension (OHT).
   Patients with primary open-angle glaucoma or OHT were included provided

Version date: 02 February 2023

they were on stable monotherapy bilaterally with IOP controlled ( $\leq$  21 mmHg) in both eyes. Any topical IOP-lowering medications must have had a start date of  $\geq$  3 months prior to Screening Visit date and dosage that was not expected to change during the study.

 Was able to follow study instructions and was likely to complete all required visits

### 6.2.2 Exclusion Criteria

Patients that have any of the following criteria will be excluded:

- Have uncontrolled severe systemic disease that, in the assessment of the
  investigator, would put safety of the participant at risk through participation, or
  which would prevent or confound protocol-specified assessments
  (e.g., hypertension and diabetes, Sjögren's syndrome, rheumatoid arthritis,
  systemic lupus erythematosus, immunodeficiency disease, etc.)
- Known allergy or sensitivity to the study products or their components
- Females who were pregnant, nursing, or planning a pregnancy
- Females of childbearing potential and who were not using a reliable method of contraception
- Current enrollment in an investigational drug or device study or participation in such a study within 30 days of entry into this study at Screening Visit
- Schirmer Test (with anesthesia)  $\leq 2$  mm in either eye at Screening Visit
- Patient anticipated contact lens wear during the study, or the patient had worn contact lenses in the last 3 months prior to Screening Visit
- Any scheduled or planned elective ocular or systemic surgery or procedure during the study, which in the investigator's opinion, may have impacted the patient's study participation
- At the Screening and Baseline visits, either eye has corneal staining score of 5 in any of the 5 zones or a total score of > 19 based on the modified NEI grading scheme (score range = 0 to 5; graded in 5 zones of the cornea for a total score range of 0 to 25) or conjunctival staining score of 5 in any of the

Version date: 02 February 2023

6 zones based on the modified NEI grading scheme (score range = 0 to 5 per zone)

- Use of systemic medications (over-the-counter, herbal, prescription, or nutritional supplements for dry eyes), which may have affected tear film or vision (including but not limited to the following: flax seed oil, fish oil, omega-3 supplements, cyclosporine, antihistamines, cholinergic agents, anticholinergics, antimuscarines, beta-blocking agents, tricyclic antidepressants, phenothiazines, estrogen-progesterone, and other estrogen derivatives), unless that medication had been used at the same dose for at least 3 months prior to screening and the dosage was not expected to change during the course of the study
- Presence of 1 or more of the following ocular conditions in at least 1 eye:
  - Active ocular infection or non-keratoconjunctivitis sicca (KCS) ocular inflammation
  - Active ocular allergy
- History of recurrent herpes keratitis or active disease within 6 months prior to Screening Visit
- Corneal disorder or abnormality that affected corneal sensitivity or normal spreading of the tear film (except superficial punctate keratitis)
- Severe blepharitis or obvious inflammation of the lid margin, which in the judgment of the investigator, may have interfered with the interpretation of the study results
- Keratoconjunctivitis sicca secondary to the destruction of conjunctival goblet cells, such as occurs with vitamin A deficiency or scarring such as that with cicatricial pemphigoid, alkali burns, Stevens-Johnson syndrome, trachoma, or irradiation
- Substantial non-KCS keratitis with overlying corneal stain or other significant corneal findings not directly related to dry eye; in addition, patients with dry eye signs/symptoms (e.g., filamentary keratitis) of a severity where topical monotherapy with an artificial tear would have been inappropriate
- Occlusion of the lacrimal puncta for either eye, with punctal plugs or cauterization < 3 months prior to Screening Visit

Version date: 02 February 2023

- History of prior ocular/ophthalmic surgery or trauma, which could affect corneal sensitivity and/or tear distribution (e.g., cataract surgery, laser-assisted in situ keratomileusis [LASIK], photorefractive keratectomy, or any surgery involving a limbal or corneal incision) within 6 months prior to at Screening Visit
- Patients who were currently using topical ocular medication or had used topical ocular medication within 2 weeks of Screening Visit; however, patients who were being treated bilaterally with the following could have been considered:
  - Current use of a marketed artificial tear, which was to have been discontinued at the Screening Visit
  - Monotherapy for glaucoma or OHT using a prostaglandin analog, betablocker, alpha-2 agonist, or carbonic anhydrase inhibitors; any topical IOP-lowering medications must have had a start date of ≥ 3 months prior to Screening Visit and the dosage was not expected to change during the study
  - If using any form of topical ophthalmic cyclosporine (i.e., RESTASIS®), lifitegrast 5% ophthalmic solution (Xiidra®), for less than 90 days prior to Screening Visit
- Patients who were currently being treated with both IOP-lowering medication and any form of topical ophthalmic cyclosporine (i.e., RESTASIS®) or lifitegrast 5% ophthalmic solution (Xiidra®) or generic of these medications cannot be enrolled
- Patient had a condition or is in a situation, which in the investigator's opinion, may have put the patient at significant risk, may have confounded the study results, or may have interfered significantly with the patient's participation in the study

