#### 6.3.3 Data Collection Methods

Eligible participants will be provided an IRB approved ICF. The physician or their staff will record any relevant patient information per standard of care (SOC) into their local patient health record keeping system. Patient eligibility, required demographics and additional visit information will be recorded in supplied paper study data forms (Appendix B). In addition, any applicable safety reporting will be recorded on the

Version date: 02 February 2023

supplied paper AE/SAE forms (Appendix F) and follow the process outlined in Section 9.3.

Paper English versions of the OSDI, Current Symptom Survey, Patient Eye Drop Experience Survey and the Study Product Usage Questionnaire will be provided to the site and labeled with a unique patient number for completion by the patient. Consented patients who meet all inclusion and none of the exclusion criteria will be allowed to complete these questionnaires at the specified study days. The participating site will be asked to send the completed questionnaires regularly to Lumanity (see Appendix A).

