### 6.4 Treatments

#### 6.4.1 Treatments Administered

During the treatment phase, each patient will be instructed to instill 1 to 2 drops of ABBV-444 in each eye, as needed, but at least 2 times daily. The same vial can be used for both eyes and should be used one time only. The used vial should then be stored in the supplied collection bag and returned to the site at the next scheduled visit for drug accountability, Section 6.4.5.

Patients are to be instructed during Screening Visit to not use any eye drops (artificial tears or prescription) for at least 4 hours prior to their Baseline Visit. If the patient is concurrently using allowed RESTASIS or IOP-lowering therapy drops during the study treatment they are to be instructed to wait a minimum of 15 minutes between administration of study drug and the allowed concomitant eye drops.

Version date: 02 February 2023

Table 2. Identity of Investigational Product

Investigational Product	ABBV-444
Mode/Route of Administration	Ophthalmic
Dosage Form	Solution, Single Dose Vial
Strength	Carboxymethylcellulose Sodium and Glycerin Ophthalmic Solution Preservative Free with Potassium Chloride
Frequency of Administration	Minimally BID
Storage Conditions	Between 15°C and 30°C (59 – 86°F)

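### The cyclosporine/lifitegrast exception in the topical-medication exclusion has its 90-day limit reversed, so read literally no user of these drops is eligible or can enter the FAS

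*Combined protocol and SAP*

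**What the plan says.** - **Inclusion (Section 6.2.1, repeated in the Synopsis).** For topical cyclosporine or lifitegrast, "participants must be using the drops for ≥ 90 days prior to the Screening Visit". They must also intend to stay on them unchanged throughout the study.
- **Exclusion (Section 6.2.2).** Current use of topical eye medication, or use within 2 weeks of Screening, excludes a patient. The criterion then relaxes this: "patients who were being treated bilaterally with the following could have been considered". Three items follow: a marketed artificial tear that is stopped at Screening; single-agent IOP-lowering therapy started at least 3 months earlier; and cyclosporine or "lifitegrast 5% ophthalmic solution (Xiidra®), for less than 90 days prior to Screening Visit". The Synopsis has the same third item, "for less than 90 days prior to Screening Visit".
- **Combination bar (Section 6.2.2).** A separate criterion starts "Patients who were currently being treated with both IOP-lowering medication" and excludes those who also use cyclosporine or lifitegrast.
- **How the criteria combine (Section 6.3.3).** "Consented patients who meet all inclusion and none of the exclusion criteria will be allowed to complete these questionnaires".
- **Dosing (Section 6.4.1).** A patient who is "concurrently using allowed RESTASIS" or IOP-lowering drops must leave at least 15 minutes between those drops and the study drug.
- **Analysis (Sections 7.1 and 7.3.3).** The FAS takes subjects who qualify on the inclusion and exclusion criteria and finish 30 days of treatment. The primary analysis of OSDI change uses the FAS. Section 7.1 defines no other set.

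**The concern.** An exception to an exclusion should let in the patients whom the inclusion criteria want. This one lets in recent starters, whom the inclusion criterion rejects, and leaves out stable users, whom the inclusion criterion accepts.

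Two things are at stake. A site that applies the text as written would turn away patients the protocol means to take. A site that follows the intent would enrol stable users who, on paper, breach an exclusion criterion. Because FAS membership depends on eligibility, such a patient who completes 30 days is out of the primary analysis on the literal text and in it on the intended text. The study is open-label with one arm, so that choice could be made after the OSDI results are known.

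**Working it through.** This is a check of logic. The only planning figure nearby is the evaluable number, so that comes first.

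**The plan's own figure (Section 7.2).** 40 enrolled, 10% non-response: 40 × (1 − 0.10) = 36. It reproduces, and the eligibility wording does not enter into it.

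**Eligibility rule.** From Section 6.3.3, eligible = passes inclusion AND NOT excluded. For a user of these drops with *d* days of use at Screening, all other criteria being met:

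- passes inclusion if *d* ≥ 90 (Section 6.2.1);
- excluded by the topical-medication criterion unless an exception applies (Section 6.2.2);
- literal exception: *d* < 90; corrected exception: *d* ≥ 90.

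| Days of use | Passes inclusion | Literal: exception applies | Literal: eligible | Corrected: exception applies | Corrected: eligible |
|---|---|---|---|---|---|
| 30 | no | yes | no | no | no |
| 89 | no | yes | no | no | no |
| 90 | yes | no | **no** | yes | **yes** |
| 180 | yes | no | **no** | yes | **yes** |

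Literally, eligibility needs *d* ≥ 90 and *d* < 90 at once, which no value satisfies. Non-users of these drops are unaffected. Of the three classes (non-user, under 90 days, 90 days or more), only the last changes status.

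**Alternative reading.** Suppose the item is really a stand-alone exclusion that was indented one level too far. A bar on use under 90 days then agrees with inclusion. But the topical-medication criterion now has no exception at all for these drops, so users at 90 and 180 days are still excluded. The result is the same for all three classes.

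**Intent.** Three places show that stable users were meant to enter:

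- Section 6.4.1 tells patients how to space permitted cyclosporine and the study drug.
- The combination bar would be redundant if every user of these drops were already excluded.
- The neighbouring IOP-lowering exception, and the systemic-medication exclusion, both accept treatment that has been stable for at least 3 months.

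**Illustration of size.** The protocol does not give the share *s* of stable users. Assume *s* among the 36 evaluable subjects and an unchanged SD. The literal FAS is 36 × (1 − *s*), and the standard error of the mean OSDI change is multiplied by √(1/(1 − *s*)).

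| Assumed *s* | Literal FAS | SE multiplier |
|---|---|---|
| 0% | 36 | 1.00 |
| 5% | 34.2 | 1.03 |
| 10% | 32.4 | 1.05 |
| 20% | 28.8 | 1.12 |
| 30% | 25.2 | 1.20 |

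**The case against.** The strongest reply is that the number may be right and the bullet level wrong. The other two exceptions name a treatment, whereas this one is phrased as a condition. It reads naturally as a separate exclusion that mirrors the inclusion rule. The Synopsis text has lost its indentation, so it cannot settle the question. This is a fair account of how the error may have arisen, but it does not rescue the text: stable users would still have no exception to the topical-medication bar.

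Second, the intent is plain, and a single site would probably enrol stable users anyway. The FAS loss then needs someone to apply the criterion literally after enrolment, and the protocol describes no such review. This stands as a limit on the likely harm. The FAS definition nevertheless points to the written criteria, so the text should agree with the practice.

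Third, no effect can be shown from the documents. That is correct. The user shares above are assumptions, the study is descriptive, and no power or error rate depends on this point.

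Two smaller points also stand. Section 6.4.1 names only the cyclosporine product, so for lifitegrast the evidence of intent comes from the inclusion criterion and the combination bar. And the lead-in to the exceptions requires bilateral treatment, which the inclusion criterion for these drops does not mention.

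**Conclusion.** The concern holds. As written, the inclusion criterion and the topical-medication exclusion together shut out every cyclosporine or lifitegrast user, whether the faulty bullet is taken as an exception or as a misplaced exclusion. The class wrongly affected is stable users of 90 days or more who meet all other criteria and are not on IOP-lowering drops. Users under 90 days and non-users keep their status.

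The error should be corrected because the same criteria define the primary analysis set. Its practical size is unknown: nil if no such patients present, and otherwise dependent on a share the protocol does not state. The planned 40 and about 36 stand.

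**What to change.** In the Synopsis exclusion criteria and in Section 6.2.2, change the third exception to: topical ophthalmic cyclosporine or lifitegrast 5%, used for at least 90 days before the Screening Visit, with no change planned during the study. If the sponsor wants an explicit bar on use under 90 days, list it as a separate exclusion outside the exceptions. While editing, confirm whether bilateral use is meant to be required for these drops, since the lead-in would impose it. The combination bar can stay as it is.

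Section 7.1 then needs no change on this point: stable users who meet the remaining criteria and complete 30 days belong to the FAS. The cost is one bullet corrected in two places, with no extra data, visits or analyses.
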